As part of our policy for addressing risk and prioritising the welfare of participants, participants are provided with links to online support, access to contact the trial team, and automatic signposting to help and guidance if reporting risk (e.g., suicidal thoughts, as indexed in items within outcome measures such as the Patient Health Questionnaire-9, PHQ-9 on the screening or follow-up websites) or levels of symptoms suggesting a need for help within any of the assessments within the cohort study. These messages include general information on the presenting symptom, recommended actions to make themselves safe, and advice to seek medical help, and direct links to relevant national sources of help.

The main indicators of harm will be the completion of questionnaires by the participants at all assessments (baseline, 6 weeks, 12 weeks). Questionnaires will be automatically screened for signs of severe distress (for example, defined as scores above 20 on PHQ-9 for depression or reports of suicidal ideation), with automatic programmed questions following up to ascertain aspects of risk and to automatically provide users with recommended advice and signpost towards help (family doctor, local hospital, relevant charities; e.g., website link to the Samaritans in the UK. Other indicators would be report of worsening symptoms or suicidality in direct contact from participants to the research team. Individuals reporting severe levels of symptoms or meeting diagnostic criteria for depression will be offered guidance to seek appropriate help from their GP/family doctor, occupational health or student well-being service should this seem necessary.

For those who enter the trial and then indicate risk there will be the option to contact a site researcher via e-mail or telephone to seek advice. This advice will include guidance to seek appropriate help from their GP/family doctor, occupational health or student well-being service should this seem necessary. Project researchers will be trained in and provided with a protocol to assess risk and with standard useful responses in these circumstances (see Section 14 on Risk Management). The trial site has a designated senior clinician [clinical psychologist or CBT Therapist] who will be available as a resource to researchers to provide guidance on clinical issues arising from participants either through

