standardized measures or contacts initiated by the participant. If the researcher has serious concerns about a participant, where appropriate, after discussion with the clinician, the clinician will contact the participants (by email, telephone) to review the situation, provide guidance and offer to write a referral letter, subject to participant consent. These procedures will be made explicit in all information sheets. Any concerns detected this way will be recorded on a standardised pro forma, a copy which will be sent to the sponsor for the trial. The same process will be activated in response to any concerns raised by participants at other times, either spontaneously or in responses during the assessments. We will record both serious and non-serious adverse events as defined by the National Research Ethics Service (e.g. deaths; self-harm; serious violent incidents, referral to crisis care or admission to psychiatric hospital) within both groups and report them to the Research Ethics Committee to determine whether events are related to the treatments and to take appropriate action.

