13.2 Definitions

Standard definitions for adverse events etc are in the table below. Because the current interventions are digital self-help rather than a medicinal product and involve no biological agent, it is not appropriate to define adverse events etc re any untoward medical occurrence – rather as a psychological intervention, appropriate adverse events would include those related to mental state and behaviour:

- i) Serious adverse events (SAEs) including death, suicide attempt, self-harm, serious accident or violent incident, referral to crisis care or admission to psychiatric hospital.
- ii) Adverse Events (AE) may include significant worsening symptoms of anxiety, worsening symptoms of depression, as operationalized by a reliable deterioration of movement from 'mild' to 'severe' or 'moderate' to 'severe' levels of symptoms on GAD7 or PHQ9 AND a change of ≥4 points on GAD7 or ≥6 points on PHQ9 from baseline assessment to 6 weeks assessment or from 6 weeks assessment to 12 weeks assessment, new instance of self-harm, new instance of suicidality.

The following definitions are therefore adapted in light of this – see **Table 12**.

Table 12 Definitions of Events

Term	Definition
Adverse Event (AE)	Standard: Any untoward medical occurrence in a participant to whom a medicinal product has been administered, including occurrences which are not necessarily caused by or related to that product. Adapted: Any deterioration in mental state or behaviour in a participant to whom the intervention has been administered, including occurrences which are not necessarily caused by or related to the intervention.

Adverse Reaction (AR)

Standard: An untoward and unintended response in a participant to an investigational medicinal product which is related to any dose administered to that participant.

The phrase "response to an investigational medicinal product" means that a causal relationship between a trial medication and an AE is at least a reasonable possibility, i.e,. the relationship cannot be ruled out.

All cases judged by either the reporting medically qualified professional or the Sponsor as having a reasonable suspected causal relationship to the trial medication qualify as adverse reactions.

Adapted: An untoward and unintended response in a participant to an intervention which is related to any dose of the intervention administered to that participant.

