The phrase "response to an intervention" means that a causal relationship between an intervention and an AE is at least a reasonable possibility, i.e. the relationship cannot be ruled out.

All cases judged by either the reporting appropriately clinically qualified professional or the Sponsor as having a reasonable suspected causal relationship to the intervention qualify as adverse reactions.

Serious Adverse Event (SAE)

Standard: A serious adverse event is any untoward occurrence that:

- results in death
- is life-threatening
- requires inpatient hospitalisation or prolongation of existing hospitalisation
- results in persistent or significant disability/incapacity
- consists of a congenital anomaly or birth defect

Other 'important events' may also be considered serious if they jeopardise the participant or require an intervention to prevent one of the above consequences.

NOTE: The term "life-threatening" in the definition of "serious" refers to an event in which the participant was at risk of death at the time of the event; it does not refer to an event which hypothetically might have caused death if it were more severe.

Serious Adverse Reaction (SAR)

Standard: An adverse event that is both serious and, in the opinion of the reporting Investigator, believed with reasonable probability to be due to one of the trial treatments, based on the information provided.

Suspected Unexpected Serious Adverse Reaction (SUSAR)

Standard: A serious adverse reaction, the nature and severity of which is not consistent with the information about the medicinal product in question set out in the reference safety information:

- in the case of a product with a marketing authorisation, this could be in the summary of product characteristics (SmPC) for that product, so long as it is being used within it's licence. If it is being used off label an assessment of the SmPCs suitability will need to be undertaken.
- in the case of any other investigational medicinal product, in the investigator's brochure (IB) relating to the trial in question

Adapted: A serious adverse reaction, the nature and severity of which is not consistent with the information about the intervention in question set out in the reference safety information

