13.3 Recording and reporting of SAEs, SARs AND SUSARs

[figure not shown]
All serious adverse events that are trial or treatment related will be recorded and immediately reported to the Chief Investigator and within 1 working day (24 working hours) to the ExeCTU Trial Manager. If these are also classed as unexpected, they will be reported to the relevant ethics committees.

We will, in line with other complex intervention studies, monitor non-serious adverse events, serious adverse events that are not trial or treatment related, serious deterioration, and active withdrawals from treatment, with specific questions in the follow-up and in response to specific participant-initiated reports. Symptoms of depression or anxiety will not be defined as adverse events unless suicidal ideation, plans or an attempt has been made. The reporting period for all events and reactions will be from referral to 12weeks post baseline follow-up. Data on any adverse events will be collected by a member of the research team at each assessment and entered directly into the EDC.

The SAE form will capture the following data:

- Date and time of onset
- Date and time investigator became aware
- SAE category
 - o Death i.e. (homicide, suicide, accident, illness, all appropriate options) etc.)
 - Life threatening i.e. (suicide attempt, serious assault, self- harm)
 - o Hospitalisation or prolongation of existing hospitalisation or referral to crisis team
 - Persistent or significant disability or incapacity i.e. (include development of problematic substance/ alcohol abuse; onset of new Axis I disorder)
 - Congenital anomaly or birth defect
 - Other i.e. (potentially dependent life events, e.g. job loss divorce)
- The intensity will be specified as mild, moderate or severe
- The SAE will be determined as intermittent or continuous
- The SAE will be determined as expected or unexpected
- The SAE outcome will be determined as resolved with a date provided, resolved with sequelae, ongoing (follow ups to the SAE will be provided when there is a change to report in participants condition) or died (if died the cause of death will be specified)
- The SAE relationship to the study or trial procedures will be determined as not related, unlikely to be related, possibly related, definitely related or unknown
- A detailed description of the event will be provided and this field will also be used to
 document the dates and number of attempts made to contact a participant by phone and/or

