13.4 Responsibilities

Researchers at central site (University of Exeter) to check for SAEs, AEs and ARs when participants complete treatment or at follow-up, potentially in response to automated feedback from website.

Chief Investigator (CI) is responsible via liaison with research team at central site for:

- 1. Ensuring that all SAEs are recorded in EDC and reported to the ExeCTU Trial Manager within 24 working hours / 1 working day of becoming aware of the event and provide further follow-up information as soon as available.
- 2. Ensuring that SAEs are chased with ExeCTU Trial Manager if a record of receipt is not received within 2 working days of initial reporting.
- 3. Ensuring that AEs and ARs are recorded and reported to the ExeCTU Trial Manager in line with the requirements of the protocol.
- 4. Immediate review of all SUSARs.
- 5. Review of specific SAEs and SARs in accordance with the trial risk assessment and protocol as detailed in the Trial Monitoring Plan.

Sponsor (NB where relevant these can be delegated to CI and trial manager) is responsible for:

- 1. Central data monitoring and verification of AEs, ARs, SAEs, SARs and SUSARs according to the trial protocol within the database (EDC).
- 2. Reporting safety information to the CI, delegate or independent clinical reviewer for the ongoing assessment of the risk / benefit according to the Trial Monitoring Plan.
- 3. Reporting SAEs that are related to the trial and unexpected, by email to the research ethics committee.
- 4. Reporting SAEs that are related to the trial and unexpected, by email to the research ethics committee.
- 5. Reporting safety information to the independent oversight committees identified for the trial (Data Monitoring Ethics Committee (DMEC) and / or Trial Steering Committee (TSC)) according to the Trial Monitoring Plan.
- 6. Expedited reporting of SUSARs to the Competent Authority (MHRA in UK) and REC within required timelines.
- 7. Notifying Investigators of SUSARs that occur within the trial.
- 8. Preparing standard tables and other relevant information in collaboration with the CI and ensuring timely submission to the MHRA and REC.

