14.3 Identifying Suicide Risk

These are 3 ways that that a recruit or participant could indicate risk to the research team (1) during a screening/follow-up assessment, (2) raised with the trial PWP providing 'on demand' support (3) providing to the facilitator or in direct contact with a trial researcher by phone, text or email.

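### Table 12 ties a non-serious adverse event to having been given the intervention, which contradicts the both-arm recording promised elsewhere in the Protocol

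*Protocol*

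**What the plan says.** Protocol 13.2 presents Table 12 as the definitions adapted for a psychological intervention. Its adapted AE row reads "Any deterioration in mental state or behaviour in a participant to whom the intervention has been administered", whether or not the event is related to the intervention. The SAE row starts "A serious adverse event is any untoward occurrence that" and does not depend on exposure.

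Item (ii) of 13.2 lists what an AE may include: a defined worsening on GAD-7 or PHQ-9 "from baseline assessment to 6 weeks assessment or from 6 weeks assessment to 12 weeks assessment", and new self-harm or suicidality. It names no arm.

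Other sections are wider than Table 12:

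- 13.1 has serious and non-serious events recorded "within both groups and report them to the Research Ethics Committee to determine whether events are related to the treatments", and makes the questionnaires at baseline, 6 and 12 weeks the main signal of harm.
- 13.3 states that "Data on any adverse events will be collected by a member of the research team at each assessment", with a reporting period running from referral to the 12-week follow-up. It also says that depression or anxiety symptoms are not AEs unless there is suicidal ideation, planning or an attempt.
- The procedures schedule in 8.11 places AE assessments at 6 and 12 weeks for everyone.

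On detection, 14.3 lists three ways in which risk can reach the team. One is that it is "raised with the trial PWP providing 'on demand' support". Under 9.2 the DTC arm receives the intervention only once the first arm has finished its six weeks. The intervention description in 9.1 adds that the last DTC group is treated outside the study.

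**The concern.** The AE row keeps the exposure clause of the medicinal-product definition printed beside it. In a drug trial that clause separates treated from untreated people. Here it cuts across the randomised comparison, because before crossover the DTC arm is untreated by design. A DTC student who deteriorates in week 4, or an sbLICBT student who deteriorates without ever starting, meets the AE definition under 13.1 and not under Table 12.

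Weeks 0-6 are the only period in which one arm is treated and the other is not, so they supply the concurrent background rate. Section 12.7 would discontinue the trial if evidence of harm accumulates, and that judgement needs a control count made under the same definition. Staff working from different sections could log different events for the same arm.

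A second, smaller issue is that PWP support contact goes with receiving the intervention. In weeks 0-6 it can bring events to light in one arm only.

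**Working it through.** The Protocol gives no AE rate and no sample size calculation, so there is no figure to reproduce. The check sets the texts side by side and then counts the observation time that depends on which one governs.

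**Who can have a non-serious AE, and from when**

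| Text | Population | Start |
|---|---|---|
| Table 12, adapted AE row | those given the intervention | receipt of the intervention |
| 13.2(ii) | no restriction | baseline |
| 13.1 | both groups | not stated |
| 13.3 | no restriction | referral |
| 8.11 schedule | no restriction | assessed at 6 and 12 weeks |

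Table 12 stands alone against the other four.

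**Observation time at stake**

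Inputs: 120 participants (12.2) and 1:1 allocation (8.4), so 120 / 2 = 60 per arm; DTC treatment after the first arm's six weeks (9.2). For simplicity, assume that sbLICBT participants start at baseline, that follow-up is complete, and that time before randomisation is ignored.

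- Weeks 0-6, both-groups reading: 60 x 6 = 360 person-weeks in each arm.
- Weeks 0-6, literal Table 12: 360 in sbLICBT and 0 in DTC.
- Weeks 0-12, both-groups reading: 60 x 12 = 720 in each arm.
- Weeks 0-12, literal Table 12: 720 in sbLICBT. DTC has 60 x 6 = 360 if all start at week 6, or 30 x 6 = 180 if the last 30 are treated outside the study.

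**Detection in weeks 0-6**

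Let q be the share of events found by the scheduled assessments, equal in both arms, and e the share of the remainder found through PWP contact in sbLICBT only. With equal true rates,

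observed ratio = [q + (1 - q)e] / q = 1 + (1 - q)e / q.

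The documents give neither q nor e. For assumed q of 0.6 to 0.9 and e of 0.1 to 0.5, the ratio runs from 1 + 0.1 x 0.1 / 0.9 = 1.01 to 1 + 0.4 x 0.5 / 0.6 = 1.33. Only the direction follows from the Protocol. The formula also applies only to events that a support contact can reveal. An AE defined by a change in score between two assessments cannot arise that way.

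**The case against.** The strongest reply is that the clause is left over from the standard wording and that the operative text overrides it: both groups in 13.1, collection at every assessment in 13.3, the common schedule in 8.11, and the unrestricted criterion in 13.2(ii). This stands to the extent that the fault is a contradiction. A reader might infer from Table 12 that control-arm AEs would be zero before crossover whatever the true rate. The Protocol as a whole does not provide for that, and SAEs are not affected.

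Detection is also largely shared. The questionnaires are the main route, both arms can contact the team, and the follow-up suicidality questions in 14.3.2 are automated and identical for everyone. A reader might infer that counts by arm cannot be compared at all. That goes too far, because the one-sided route is secondary and is confined mainly to weeks 0-6.

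A reader might also see asymmetry in 13.4, which asks researchers "to check for SAEs, AEs and ARs when participants complete treatment or at follow-up". But 8.10 and the column headings in 10.3 equate treatment end with the 6-week assessment, which both arms complete.

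Finally, this is a feasibility trial, and the Protocol sets out no formal between-arm test of AEs. That limits the consequences. It does not remove the need for one definition behind the 12.7 judgement.

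**Conclusion.** The point holds as a contradiction to be corrected. The adapted AE row limits non-serious AEs to exposed participants, while 13.1, 13.3 and the 8.11 schedule do not. What depends on it is whether 360 person-weeks of untreated control observation in weeks 0-6 count, given 60 per arm and complete follow-up. Events in sbLICBT participants who never start depend on it too, and their number is unknown.

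The uneven PWP route in weeks 0-6 is real but secondary. Its effect cannot be derived from the documents. Use of on-demand support is itself a feasibility outcome in 10.1, and the range shown above reflects assumed inputs, so no inflation ratio should be reported as a finding.

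**What to change.** 1. In the adapted AE row of Table 12, replace the exposure clause with: *in any trial participant, in either arm, whether or not the intervention was received, over the reporting period in 13.3*. Referring to 13.3 matters, because a start at randomisation would conflict with its start at referral.
2. Reconcile 13.2(ii), which counts a defined worsening of symptoms as an AE, with the 13.3 statement that symptoms of depression or anxiety are not AEs unless suicidality is present. Which rule applies is for the trial team to settle.
3. After that, base the between-arm AE comparison on events found by the identical questions and scores at the scheduled 6- and 12-week assessments.
4. List separately the events that surfaced only through PWP or group contact. A source-of-report field would help but is optional; the free-text event description on the SAE form and the 14.10 risk register already capture part of this.

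The cost is one clause, one reconciliation of text and one tabulation rule. No additional assessment is needed.

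### Table 12 applies a stricter causality test, by a different judge, to a serious adverse reaction than to an adverse reaction, and the SUSAR definition inherits it

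*Protocol*

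**What the plan says.** Section 13.2 states that the standard definitions are adapted because this is a psychological intervention. Table 12 then gives these rows:

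- **Adverse reaction (AR), adapted.** The causal relationship "is at least a reasonable possibility, i.e. the relationship cannot be ruled out". The judges are alternatives: "All cases judged by either the reporting appropriately clinically qualified professional or the Sponsor".
- **Serious adverse reaction (SAR), standard wording only.** The event is serious and, "in the opinion of the reporting Investigator", is "believed with reasonable probability to be due to one of the trial treatments". No adapted version is given.
- **SUSAR.** "Adapted: A serious adverse reaction, the nature and severity of which is not consistent with the information about the intervention in question" (the definition then points to the reference safety information).

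In 13.3 the SAE form grades relatedness as "not related, unlikely to be related, possibly related, definitely related or unknown". The same section opens its reporting rule with "All serious adverse events that are trial or treatment related will be recorded and immediately reported to the Chief Investigator" and adds "If these are also classed as unexpected, they will be reported to the relevant ethics committees". Section 13.4 gives the Sponsor expedited reporting of SUSARs to the competent authority and the REC.

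**The concern.** A reader expects a serious adverse reaction to be an adverse reaction that is also serious. In Table 12 it is not. Between the two rows the threshold rises from possibility to probability, and the Sponsor loses its independent say. If the Sponsor judges a causal link reasonably possible and the Investigator does not think it probable, the event is a serious AE and an AR, yet not a SAR.

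The SUSAR row builds on the SAR row, so a category meant for suspected reactions takes on the stricter test. The consistency of the SAR and SUSAR counts is at stake, together with the one reporting route that depends on the SUSAR label. The events in question include self-harm and suicide attempt, which 13.2 lists as serious.

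**Working it through.** No sample size, rate or error probability is involved, so there is no figure to reproduce. The check sets the provisions side by side.

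**1. The definitions**

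| Row of Table 12 | Threshold | Judge | Adapted to this trial? |
|---|---|---|---|
| AR | reasonable possibility, not ruled out | clinically qualified reporter or Sponsor | yes |
| SAR | reasonable probability | reporting Investigator | no |
| SUSAR | inherits SAR | inherits SAR | yes, but built on SAR |

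**2. The five form levels against the two thresholds**

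| Level on the SAE form | Meets AR? | Meets SAR? |
|---|---|---|
| not related | no | no |
| unlikely | not naturally a reasonable possibility | no |
| possibly related | yes | not necessarily |
| definitely related | yes | yes |
| unknown | arguably, as not ruled out | not on its face |

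The rows diverge firmly on one level (possibly related) and arguably on a second (unknown). No level corresponds to reasonable probability, and the visible text does not say which levels count as related. The form also asks about relationship to the study or its procedures, whereas the SAR row asks about the trial treatments.

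**3. Tracing a serious, unexpected event rated possibly related**

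- It meets the AR threshold.
- Read literally, it need not meet the SAR threshold.
- If it is not a SAR, it is not a SUSAR.
- The expedited SUSAR route in 13.4 is then not triggered.

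**4. Which reporting triggers use the SAR wording**

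| Provision | Trigger | Depends on SAR row? |
|---|---|---|
| 13.1, report to REC | serious and non-serious events, so that relatedness can be determined; no timeline | no |
| 13.3, immediate report to CI and Trial Manager report within 1 working day | related SAEs | no, but related is undefined |
| 13.3, ethics report | related and unexpected | no, but related is undefined |
| 13.4, CI duty to report to Trial Manager within 1 working day | all SAEs | no |
| 13.4, Sponsor report to REC | related and unexpected | no, but related is undefined |
| 13.4, expedited report to competent authority and REC | SUSAR | **yes** |
| 12.7, stopping rule | cumulative evidence that the intervention may cause harm | no |

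Only one trigger inherits the stricter test. The table also shows a second inconsistency: 13.3 words the one-working-day report for related SAEs, while 13.4 requires it for all SAEs.

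**The case against.** The strongest objection is that little turns on the mismatch. A reader might infer that a serious event rated possibly related would escape escalation altogether. The documents do not support that. Section 13.4 sends every SAE to the Trial Manager within 1 working day. Under 13.3 the CI signs each SAE form and assesses its safety implications. Section 13.1 reports events, with self-harm as a named example, to the REC. Suicide-risk answers at follow-up alert the CI automatically (14.3.2), and deaths are reported whatever their cause (13.5). This stands, and it confines the consequence to SAR and SUSAR labelling and the expedited route.

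A reader might also infer that the stopping rule is weakened. It is not tied to SAR counts: 12.7 speaks of evidence that the intervention may cause harm.

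Nor should the divergence be stretched to three of the five form levels by counting unlikely as an adverse reaction. Taken alone, the phrase about not ruling out a relationship could reach that far, but the same sentence requires at least a reasonable possibility, which an unlikely relationship does not naturally meet.

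Finally, the safety flow chart (Figure 2) and the Trial Monitoring Plan are not visible, and either could map form levels to related. That limits what can be said about the mapping. It does not remove the conflict between two rows of Table 12, both of which are visible. The missing adapted SAR text suggests a template row left unrevised rather than a deliberate stricter rule, but it is still the operative wording.

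**Conclusion.** The inconsistency is real and of low severity. The AR and SAR rows differ in both threshold and judge, and SUSAR follows the SAR row. The practical exposure is an unexpected serious event rated possibly related, and arguably one rated unknown. Such an event could be left out of the SAR and SUSAR counts and miss the expedited SUSAR route.

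This rests on a literal reading of probability as stricter than possibility, and on the visible text only. With 120 participants screened for low symptoms and low risk, few SAEs are likely (an assumption, since the protocol gives no expected rate), so a single event classified differently could change a reported count appreciably. The feasibility outcomes and the comparisons of BRS, PHQ-9, GAD-7 and WSAS are not affected.

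**What to change.** 1. In Table 12, replace the SAR row with an adapted definition: an adverse reaction, as defined in that table, that is also serious, judged by the same parties (reporting clinician or Sponsor). SUSAR then inherits the aligned test without further change.
2. In 13.3, state which levels of the SAE form count as related, consistently with that definition. Possibly related and definitely related follow directly. The handling of unknown should be stated explicitly, including reclassification when more information arrives.
3. Reconcile the triggers in 13.1 (events to the REC, no timeline), 13.3 (related SAEs only) and 13.4 (all SAEs to the Trial Manager), and check that Figure 2 and the Trial Monitoring Plan agree.

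The cost is a few sentences and possibly one or two more expedited reports. No data collection or analysis changes.
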